Power analysis was performed to estimate an adequate sample size to support statistical conclusion validity and so that correct inferences can be made about the relationships between study variables. The standardized effect size was calculated to equal 0.5. Assuming an alpha of 0.05, power of 0.80 and a standardized effect size of 0.5, 64 patients will be required for each treatment group based on anticipated difference in patient reported pain scores due to sciatic PNB technique. Projected sample sizes were increased approximately ten percent from 64 per group to total of 70 subjects per group in an effort to account for patient attrition and lost data, therefore, a total of 140 patients will be enrolled in the study. Additionally, if the loss in patients is unequal between groups, yielding a significant disparity between study group composition, additional subjects may be added to account for this unequal loss.

Despite the presence of multiple confounding variables, the calculated sample size is sufficient to determine if a significant difference in outcomes measures exists secondary to sciatic PNB technique. Additionally, the sample size does not need to be altered based on the equation: $N > 50 + 8k$, where N is the number of cases and k is the number of predictors (Warner, 2013). In this study there is only one predictor, sciatic PNB technique, which is anticipated to impact outcomes following ACL reconstruction.

E. Randomization:

A computer generated randomization scheme will be used to assign 70 patients to each treatment group. The randomization will be done using the maximum allowable percent deviation method. This algorithm conducts a search to find a randomization list for which all percent deviations are less than or equal to the maximum allowable percent deviation of 10%. The randomization scheme will be sent to the PI who will then prepare and maintain a log of subject assignments. The PI will notify the participating surgeon and anesthesia team of the treatment (single-injection or continuous sciatic PNB) that is to be given to the next consented patient. The research coordinator will remain blinded to the assigned treatment plan until data collection has been completed.

F. Components of Cincinnati Children's Hospital Medical Center to be Utilized for this Study:

Subjects undergoing unilateral ACL reconstruction with a hamstring autograft on an outpatient basis at the Liberty Campus of CCHMC will be recruited from the OR schedule.

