G: Data Collection:

Participants will be in the research study for approximately 4 days; the day of surgery and for follow-up phone calls once a day for the first three days after surgery. A minimum of three phone calls may be made after the patient is discharged. Once enrolled in the study, a unique study identification number will be assigned to each study participant. Assigning a unique patient identifier to each study participant allows any data gathered pertaining to them to be attached to this number rather than any patient identifiers, further ensuring that a breach in confidentiality does not occur (Polit & Beck, 2012). After obtaining written consent from the guardian(s), the medical record of the patient will be reviewed for further inclusion and exclusion criteria.

All data gathered will be used specifically for research purposes. Data collected preoperatively will include age, gender, BMI, ASA physical status, previous surgical history, self-reported tolerance of pain, self-reported level of activity since time of ACL injury, and the name of the orthopedic surgeon scheduled to perform ACL reconstruction. In addition, several questions regarding the patient's anxiety level will be asked to determine whether or not the patient has a history of anxiety that may impact pain and/or satisfaction scores postoperatively (see Appendix A). This data will be collected from the patient's medical record during the preoperative phase and directly from the patient and/or guardian(s) when appropriate. Data on study group assignment, analgesic requirement, the length of surgery, length of pneumatic tourniquet inflation time, pneumatic tourniquet inflation pressure, and systolic blood pressure at time of pneumatic tourniquet inflation will be gathered during the intraoperative phase.

In an effort to discern the impact of sciatic PNB technique on the outcome measures, data on self-reported pain scores, doses of oral pain medications, unplanned admission to the hospital due to poor pain control, and patient satisfaction will be gathered while the patient remains in the post anesthesia care unit (PACU). Data collection will then continue for 72 hours postoperatively following discharge from the PACU. Patients will document data measures on supplied data collection instruments (see Appendix B).

The patient or their guardian will record pain scores once every 6 hours for 72 hours postoperatively. In addition, the patient or their guardian will note the

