date and time their leg was no longer numb behind their knee. The orthopedic surgeon performing the ACL reconstruction or a member of his orthopedic team will prescribe all postoperative oral pain medication. The oral pain medication typically prescribed is either Percocet or Vicodin. Vicodin, a schedule 3 controlled substance, is approximately half as potent as Percocet, which is a schedule 2 controlled substance. The patient will record the time and dose of all oral pain medication taken during the 72 hours postoperative period. The patient or their guardian will also record data regarding pain associated with active knee flexion once every 12 hours for 72 hours postoperatively. In addition, the patient or their guardian will record satisfaction with pain control once every 12 hours for 72 hours postoperatively.

The research coordinator may collect all data recorded by the patient and/or their guardian via telephone interview. Data will be collected using the same data collection tool given to the study participants to avoid instrumentation and maintain interrater reliability. Untoward events, such as unplanned hospital admission, CPI catheter dislodgement, or local anesthetic toxicity, will also be noted should they occur. This information will be collected from the patient or guardian once every 24 hours by the research coordinator during the 72-hour postoperative period; the postoperative period begins at the time of discharge from the PACU.

1. Survey(s) and Questionnaire(s):

Patients and their guardian will be given data collection instruments to complete postoperatively at the time of enrollment to facilitate recall when conveying information to the study staff during telephone conversations. The data collection instruments will be available in different languages and utilized for non-English speaking patients and/or guardians. The patient and their guardian(s) will receive training regarding the data collection tool both during the time of enrollment and again prior to discharge from the hospital. At the time of enrollment, essential phone numbers, including home phone and cell phone numbers, will be collected. Should the patient and/or guardian lose the data collection sheet, additional copies can be emailed to them upon request. Hospital-approved interpreters will be utilized for non-English speaking patients and/or guardian(s).

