The hypothesis that the extended duration of analgesia offered by continuous sciatic PNB decreases the incidence of unplanned admission due to poor pain control during the initial 72 hours following hamstring autograft harvest when compared to single-injection sciatic PNB will be tested with the Chi-square test. The Chi-square test is used to determine if there is a relationship between two categorical variables (Field, 2009). As the data for this DV are categorical, the focus during analysis is placed on frequencies rather than means. The Chi-square test can be used to determine if there is a significant difference between the expected frequencies and observed frequencies in one or more categories (Field, 2009).

The hypothesis that the extended duration of analgesia offered by continuous sciatic PNB does not delay active knee flexion during the initial 72 hours following hamstring autograft harvest when compared to single-injection sciatic PNB will be tested using the Wilcoxon Mann Whitney test. The hypothesis that the extended duration of analgesia offered by continuous sciatic PNB improves patient satisfaction during the initial 72 hours following hamstring autograft harvest when compared to single-injection sciatic PNB will also be tested using the Wilcoxon Mann Whitney test. The Wilcoxon Mann Whitney test is appropriate to test both these hypotheses, as this test is designed to evaluate the difference between two treatments (single-injection sciatic PNB and continuous sciatic PNB) using data from an independent measures study (Gravetter & Wallnau, 2000). During analyses, testing may be altered based on the recommendations of the statistician to better analyze the collected data. Intention-to-treat analysis will not be employed, as this may skew results and it is often difficult to obtain outcome data for study participants who have dropped out of the study (Polit & Beck, 2012).

Prior to any analyses, the distribution of the demographic variables will be compared between the two treatment groups. All statistical tests will be two-sided with a significance level of $\alpha=0.05$ and will be conducted using SAS[®] software, (Version 9.2, Cary, NC). Following the enrollment of the initial 30 subjects (with 15 in each study group), an interim analysis utilizing the statistical tests later described will be performed to determine if statistically

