Appendix A
Preoperative Data Collection Instrument

PATIENT STUDY ID NUMBER: _____

Age (in years) on day of recruitment: _____

Gender (circle one): Male Female

BMI: _____

ASA physical status (circle one): I II

Previous surgery: Yes No

If yes, what surgery? _____

Self-reported preoperative pain score (0 = no pain, 10 = worst pain): _____

Self-reported tolerance of pain (circle one):

0 = Low tolerance of pain

1 = Moderate tolerance of pain

2 = High tolerance of pain

Self-reported level of activity since the time of ACL injury (circle one):

0 = Not active at all

1 = Not active

2 = Partially active

3 = Active

4 = Highly active

What is your level of anxiety today (0 = no anxiety, 10 = worst anxiety): _____

- Are you normally anxious (yes/no)? _____
- Do you take any prescriptive medications for anxiety (yes/no)? _____
- Are you currently, or have you in the past, seen a healthcare professional for treatment of your anxiety (yes/no)? _____

[name]

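### Baseline pain and anxiety scores and the surgeon's name are recorded, yet every planned test compares the arms without covariates; pre-specified adjustment would be a cheap improvement of uncertain size.

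*Combined protocol and SAP*

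**What the plan says.** **Sample size (Section V.D).** "The standardized effect size was calculated to equal 0.5". The plan continues: "Assuming an alpha of 0.05, power of 0.80 and a standardized effect size of 0.5, 64 patients will be required for each treatment group". The figure is raised to 70 per group, 140 in total. The section grants that several confounding variables exist. It then checks N against the rule N > 50 + 8k with k = 1, on the ground that "In this study there is only one predictor, sciatic PNB technique, which is anticipated to impact outcomes following ACL reconstruction".

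**Baseline data.** Section V.G explains the anxiety questions: they are asked to "determine whether or not the patient has a history of anxiety that may impact pain and/or satisfaction scores postoperatively". It also lists the surgeon's name among the preoperative data, without a reason. Appendix A has a field for "Self-reported preoperative pain score (0 = no pain, 10 = worst pain" and a 0-10 anxiety score for the day. It gives no reason for the pain score and, as shown, has no surgeon field. On oral medication Section V.G says: "The orthopedic surgeon performing the ACL reconstruction or a member of his orthopedic team will prescribe all postoperative oral pain medication". It adds that of the two usual products one is about half as potent as the other.

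**Analysis (Section VI.B).** Mean pain per patient goes to Pearson's correlation, and pain scores at 12-hour periods to Wilcoxon Mann Whitney tests. Oral medication goes to a t-test, unplanned admission to a chi-square test, and knee flexion and satisfaction to Wilcoxon tests. None has a covariate. Demographic distributions are compared between arms beforehand, with no stated consequence. Tests may be changed during analysis on the statistician's advice. Section V.E describes no stratification of the randomization by surgeon.

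**The concern.** The plan names anxiety as a possible influence on the primary outcome, measures it, and then does not use it. It also records a preoperative pain score on the outcome's own 0-10 scale and leaves that unused. If such variables predict postoperative pain, a model that includes them leaves less residual variance, so the same patients give a narrower confidence interval and more power. The design has little reserve at 64 evaluable patients per arm.

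The second issue is pre-specification. Baseline distributions are to be examined before the outcome tests, and the tests may be altered during analysis. If covariates are not named now, any later adjustment could be chosen after the data have been seen. Naming a short list in advance closes that route whatever the gain in power.

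For oral medication, the prescriber is the surgeon or the surgeon's team, so the documents themselves point to surgeon as a source of variation in that outcome.

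**Working it through.** **Inputs.** From Section V.D: standardized effect 0.5, alpha 0.05, power 0.80, 64 per group before attrition, 70 per group and 140 in total after it. From Section VI.B: "All statistical tests will be two-sided with a significance level of" 0.05. R², the share of variance in mean 72-hour pain explained by the covariates within arm, is not in the documents. It is an assumption, shown as a range that includes zero.

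**Step 1: the plan's own figure.** Two-sided two-sample t-test, n = 64 per arm:
- noncentrality = 0.5 × √(64/2) = 2.83, df = 126, power = 0.8015;
- at n = 63, power = 0.795.

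So 64 is the smallest n that reaches 0.80, and the stated figure reproduces. If Pearson's correlation is taken between arm (two values) and mean score, it gives the same P value as this t-test, so a linear model extends the planned test directly.

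**Step 2: adjusted analysis.** With p covariate terms and N = 128, the variance of the arm difference, relative to unadjusted and allowing for chance covariate imbalance, is about

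factor = (1 − R²) × (N − 3)/(N − 3 − p) = (1 − R²) × 125/(125 − p).

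Power follows from the noncentral t with effect 0.5/√factor and df = 126 − p. For p = 2 (preoperative pain and anxiety):

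| R² | factor | power |
|---|---|---|
| 0 | 1.016 | 0.795 |
| 0.04 | 0.976 | 0.811 |
| 0.09 | 0.925 | 0.831 |
| 0.25 | 0.762 | 0.895 |

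The comparison is 0.8015 unadjusted.

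**Step 3: break-even.** The factor equals 1 when R² = p/125. That is 0.016 for two terms (2/125), 0.04 for five (5/125) and 0.056 for seven (7/125).

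**Step 4: worst case.** At R² = 0, power is 0.798 with one term, 0.795 with two, 0.785 with five and 0.778 with seven. Five to seven terms could arise if surgeon enters the pain model as several indicators; the number of surgeons is not given.

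**Step 5: the plan's predictor rule.** Arm plus two covariates is k = 3, and 50 + 8 × 3 = 74, below both 128 and 140. At N = 140 the rule allows k up to 11 (50 + 88 = 138); at N = 128, up to 9 (50 + 72 = 122). More predictors do not call for more patients.

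**The case against.** The best case for the plan has four parts.

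- **The unadjusted test is valid.** Arm is randomized and the power is as stated. This stands. The mention of confounding variables in Section V.D is loose wording and shows no bias. Section VI.B does decline intention-to-treat, and Section V.B excludes patients with failed block or catheter placement. Those are separate matters, which covariate adjustment would not repair.
- **Preoperative pain may predict little.** It is pain before surgery; the outcome is pain after graft harvest with nerve blocks in place, and Section V describes a posttest-only design. This stands as a reason for uncertainty, and it is why R² = 0 belongs in the range.
- **Adjustment is not free.** This also stands: with five terms, an R² of 0.04 only breaks even.
- **The one-predictor sentence belongs to a sample-size check and does not specify the analysis.** True, but Section VI.B is equally without covariates.

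Two stronger readings are tempting. A reader might infer that all three variables are collected because they affect pain. The documents give a reason only for anxiety, and only as a possibility. A reader might also infer that the plan certainly throws away precision and that adjusting has no downside. Without any R² in the documents, the gain could be nil or slightly negative.

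**Conclusion.** The plan leaves a possible efficiency unused and leaves the choice of covariates open. It contains no sample-size error on this point, and the unadjusted comparison of the randomized arms is not biased by these variables.

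With two covariates at 64 per arm, the change in power runs from a loss of under 1 point (0.8015 to 0.795) if they predict nothing, through gains of about 1 point at R² = 0.04 and 3 points at 0.09, to about 9 points at 0.25. With five to seven terms, the worst case is a loss of about 2 points. These figures rest on the assumed R² values, a linear model for mean pain, the plan's effect of 0.5 and 64 evaluable patients per arm. The change is worth making because it is cheap and its possible loss is small; the size of the gain cannot be fixed from the documents.

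**What to change.** 1. In Section VI.B, define the primary comparison as a linear model of each patient's mean 72-hour pain on arm, preoperative pain score and preoperative anxiety score (both 0-10). Report the adjusted mean difference with its 95% confidence interval.
2. Keep the unadjusted comparison and the Wilcoxon tests as sensitivity analyses.
3. Replace the t-test for oral medication with a linear model of arm and surgeon. Pool small-volume surgeons by a rule fixed before the data are seen. Surgeon may also be added to the pain model, at the cost in terms shown above.
4. In Section V.D, amend the one-predictor sentence and restate the rule with the new k. N stays 140.
5. Add a surgeon field to Appendix A and list the preoperative pain score in Section V.G, so that the text and the form agree.

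The cost is a short revision of Sections VI.B, V.D and V.G and one added form field, with no additional patients. The statistical price is the small loss of power if the covariates turn out not to predict pain.

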The purpose of this research is to compare the effect of single-injection sciatic PNB to continuous sciatic PNB on 1) postoperative pain control as measured by self-reported pain scores, pain medication use, and unplanned hospital admission due to poor pain control, 2) active knee flexion, and 3) patient satisfaction with pain control following ACL reconstruction with a hamstring autograft. The results of this research have the potential to positively impact pain control for the adolescent population undergoing this surgical procedure and foster responsible utilization of limited resources.

SPECIFIC AIM 1. The first aim of the study is to explore the impact of sciatic PNB technique on hamstring donor site pain control postoperatively.

H1.a. The extended duration of analgesia offered by continuous sciatic PNB decreases pain scores during the initial 72 hours following hamstring autograft harvest when compared to single-injection sciatic PNB.

H1.b. The extended duration of analgesia offered by continuous sciatic PNB decreases oral pain medication use during the initial 72 hours following hamstring autograft harvest when compared to single-injection sciatic PNB.

H1.c. The extended duration of analgesia offered by continuous sciatic PNB decreases the incidence of unplanned admission due to poor pain control during the initial 72 hours following hamstring autograft harvest when compared to single-injection sciatic PNB.

SPECIFIC AIM 2. The second aim of the study is to explore the impact of sciatic PNB technique on active knee flexion postoperatively.

H2. The extended duration of analgesia offered by continuous sciatic PNB does not delay active knee flexion during the initial 72 hours following hamstring autograft harvest when compared to single-injection sciatic PNB.

SPECIFIC AIM 3. The third aim of the study is to explore the impact of sciatic PNB technique on patient satisfaction with postoperative pain control.

H3.1. The extended duration of analgesia offered by continuous sciatic PNB improves patient satisfaction during the initial 72 hours following hamstring autograft harvest when compared to single-injection sciatic PNB.

IV. PREVIOUS CLINICAL EXPERIENCE

Concurrent Research Studies: The Department of Anesthesiology is not currently conducting another protocol with this patient population.

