The hypothesis that the extended duration of analgesia offered by continuous sciatic PNB decreases pain scores during the initial 72 hours following hamstring autograft harvest when compared to single-injection sciatic PNB will be tested with two separate tests. Both Pearson's correlation and the Wilcoxon Mann Whitney test will be utilized to test his hypothesis, as controversy surrounds the analysis of Likert scale data. It has been argued that only nonparametric statistics should be used on Likert scale data, as the intervals between the scale values may not be equal (Jamison, 2004). Taking this into consideration, the pain scores recorded for each patient will be totaled and an average pain score will be calculated for each study participant. This will allow the data to be measured on a continuous scale, thereby meeting the criteria of Pearson's correlation. Pearson's correlation is a parametric test that measures the degree and direction of linear relationship between two variables (Gravetter & Wallnau, 2000). The Wilcoxon Mann Whitney test will also be used to analyze pain scores recorded at each 12-hour period to determine if there is a difference in outcomes related to the duration of analgesia provided by sciatic PNB technique. This test is appropriate when there is one IV with two independent groups and the DV is ordinal in nature. The Wilcoxon Mann Whitney test is a nonparametric test of the null hypothesis that two populations are the same against an alternative hypothesis. This test uses the relative position of the data in a rank ordering, rather than the actual values. Using both parametric and nonparametric tests will increase confidence when drawing conclusions should both tests lead to the same results.

The hypothesis that the extended duration of analgesia offered by continuous sciatic PNB decreases oral pain medication use during the initial 72 hours following hamstring autograft harvest when compared to single-injection sciatic PNB will be tested with the Independent Samples *t*-Test. The Independent Samples *t*-Test is appropriate when there is one IV with two independent groups and the DV is continuous in nature (Field, 2009). The Independent Samples *t*-Test is used to compare differences between separate groups when there are two experimental groups (single-injection sciatic PNB and continuous sciatic PNB) and different study participants have been used in each group (Field, 2009).

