Appendix B

Post-Discharge Data Collection Instrument

PAIN CONTROL:

Keep track of your pain score and location of pain:

Pain score: 0 = no pain, 10 = worst pain			
Pain location: F = front of knee, B = back of knee, X = both front & back			
6 hours		42 hours	
12 hours		48 hours	
18 hours		54 hours	
24 hours		60 hours	
30 hours		66 hours	
36 hours		72 hours	

Date and time the leg was no longer numb behind the knee: _____

Pain medicine prescribed (circle one): Vicodin Percocet Other: _____

Write down every time pain medication is taken:

[illegible]

ACTIVE KNEE MOVEMENT:

Rate the ability to bend the knee that was operated on:

Knee Movement	12 hours	24 hours	36 hours	48 hours	60 hours	72 hours
0 = Able to bend with no pain						
1 = Able to bend, but with pain						
2 = Too much pain to bend						

SATISFACTION:

Rate your overall satisfaction score with pain management:

Satisfaction Score	12 hours	24 hours	36 hours	48 hours	60 hours	72 hours
0 = Not satisfied at all						
1 = Not satisfied						
2 = Partially satisfied						
3 = Satisfied						
4 = Highly satisfied						

From your perspective, have you encountered any unexpected postoperative experiences?

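### H1.b counts only oral pain medication, so parenteral opioid given to a patient admitted for poor pain control goes uncounted and may pull the comparison toward no difference

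*Combined protocol and SAP*

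**What the plan says.** Section III states H1.b as: "The extended duration of analgesia offered by continuous sciatic PNB decreases oral pain medication use during the initial 72 hours". Section VI.B tests it with an independent-samples t-test in the same oral-only terms: continuous block "decreases oral pain medication use during the initial 72 hours following hamstring autograft harvest when compared to single-injection sciatic PNB".

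Data collection in section V.G follows the same limit. The PACU outcome list reads "data on self-reported pain scores, doses of oral pain medications, unplanned admission to the hospital due to poor pain control". For the period after discharge: "The patient will record the time and dose of all oral pain medication taken during the 72 hours postoperative period". The one broader item in that section, "Data on study group assignment, analgesic requirement, the length of surgery", belongs to the intraoperative phase.

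Two texts are wider. The purpose in section III speaks of pain medication use without naming a route, and Appendix B instructs "Write down every time pain medication is taken". Appendix B is, however, a form that the patient or guardian completes after discharge.

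Admission is handled separately. H1.c in section III is that continuous block "decreases the incidence of unplanned admission due to poor pain control", and section VI.B tests this with a chi-square test. No text says how an admitted patient's oral count enters H1.b.

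On timing, section V.G collects oral doses in the PACU but also says "the postoperative period begins at the time of discharge from the PACU".

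**The concern.** H1.b is meant to show whether the longer block reduces the need for other pain medication. A count limited to oral doses answers that only if nearly all postoperative analgesic is taken by mouth. That is least certain for a patient admitted because oral medication did not control the pain. If parenteral opioid then stands in for oral doses, the patient adds little to the count while in hospital, and a severe analgesic failure can score as a low user.

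This matters for the comparison when such patients are unevenly spread between arms. The protocol itself expects that: H1.c predicts more of these admissions after single injection. Section I says the single injection can last up to 24 hours, and section V.A runs the sciatic infusion for 48 hours, so any divergence would fall inside the 72-hour window. If H1.c is true and substitution occurs, H1.b loses part of the benefit it is designed to detect. Testing H1.c separately makes the admissions visible but does not correct the H1.b mean.

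**Working it through.** **The plan's own figure.** Section V.D gives alpha 0.05, power 0.80, standardised effect 0.5 and 64 per group; section VI.B makes tests two-sided. The two-sample t-test solution is 63.8, so 64, with power 0.801. The figure reproduces, but it was derived for pain scores. No sample size is given for H1.b, so 0.80 serves here only as a reference.

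**Inputs not in the documents (assumptions).**
- SD of oral use: 6 doses.
- True effect on total use: 0.5 SD = 0.5 × 6 = 3 doses.
- Analysed per arm: 64, from section V.D.
- Oral doses replaced per admitted patient: 4 to 12, net of any extra oral doses taken before or after admission.
- Excess of admissions after single injection: 1 to 8 percentage points.

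**Formulas.** Shift in the mean difference = admission excess × doses replaced. Observed effect d = 0.5 − shift / 6. Power is from the two-sided two-sample t-test at 64 per arm and alpha 0.05.

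| Admission excess | Doses replaced | Shift (doses) | Shift (SD) | Observed d | Power |
|---|---|---|---|---|---|
| none | – | 0 | 0 | 0.500 | 0.80 |
| 1 point | 4 | 0.04 | 0.007 | 0.493 | 0.79 |
| 1 point | 12 | 0.12 | 0.020 | 0.480 | 0.77 |
| 2 points | 4 | 0.08 | 0.013 | 0.487 | 0.78 |
| 2 points | 12 | 0.24 | 0.040 | 0.460 | 0.73 |
| 4 points | 4 | 0.16 | 0.027 | 0.473 | 0.76 |
| 4 points | 12 | 0.48 | 0.080 | 0.420 | 0.66 |
| 8 points | 4 | 0.32 | 0.053 | 0.447 | 0.71 |
| 8 points | 12 | 0.96 | 0.160 | 0.340 | 0.48 |

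**Could the sign reverse?** The shift must reach the full 3 doses. With 12 doses replaced, that needs an excess of 3 / 12 = 25 percentage points; with 4 replaced, 3 / 4 = 75 points. Both lie far outside the range above.

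**Check under other assumptions.** Let the coefficient of variation of oral use be 0.5 and let each excess admission lose half of its recorded oral use. The bias in SD units is excess × 0.5 / 0.5. For an excess of 2, 5 and 10 points, d is 0.48, 0.45 and 0.40, and power is 0.77, 0.71 and 0.61. A coefficient of variation of 1.0 halves the bias.

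**The case against.** The strongest reply is that the direction is an inference. A patient in severe pain may take as much oral medication as allowed before admission and resume it afterwards, so the recorded total need not be low. Nothing in the documents establishes net substitution. This stands, and the point is therefore conditional.

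A reader might infer that the PACU adds a further bias between arms. The documents do not support that. Section V.A gives both arms the same initial sciatic bolus and a continuous femoral block, the single injection can last up to 24 hours, and section V.G starts the postoperative period at PACU discharge. Little difference between arms in PACU parenteral opioid is to be expected. What remains is an incomplete measure and an unclear window.

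A reader might also infer that H1.b could reverse and favour single injection. No combination in the table does this; the most extreme leaves d = 0.34 in the expected direction.

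It is also fair that every input to the magnitude is assumed, that the population is ASA I–II outpatients, and that the lowest power shown combines the largest admission excess with the largest replacement. At 1 to 2 points the loss is small, and with equal admission rates there is little bias from admission.

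Finally, admissions are counted under H1.c and asked about every 24 hours, and Appendix B does not limit its wording to oral medication. This softens the gap. A home diary is still not an inpatient medication record, and section VI.B still analyses oral use.

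**Conclusion.** The concern holds in a limited form. H1.b is oral-only, no postoperative parenteral opioid is planned to be captured, and no rule covers the count in an admitted patient; the stated purpose is broader than this. Bias toward the null follows if two conditions are met: parenteral opioid replaces oral doses on balance, and admissions for poor pain control are more frequent after single injection.

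The documents cannot size it. Under the assumptions listed, the difference shrinks by 0.04 to 0.96 doses (0.007 to 0.16 SD). Power stays close to the reference at a low admission excess and falls materially only toward the upper end of the range. It is worth correcting because the measure does not match the purpose and the remedy is cheap, not because a large distortion has been shown.

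**What to change.** - Define the H1.b outcome as total postoperative opioid by any route, converted to one opioid-equivalent unit with a conversion table fixed in advance.
- State one 72-hour window. Section V.G must be reconciled: it collects PACU doses as outcome data but starts the postoperative period at PACU discharge.
- Take PACU and inpatient doses from the hospital record, and home doses from the diary and telephone calls.
- State that admitted patients remain in the H1.b analysis. This should be explicit because section VI.B rejects intention-to-treat analysis.
- Report the oral-only total as a supporting result, next to H1.c, so that both can be read together.

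The cost is a few added record fields, the conversion table, revised wording in sections III, V.G and VI.B, and a record request for any admission elsewhere. Record review is now described for eligibility and preoperative data, so inpatient dose retrieval would be a new task. The outcome is no longer purely oral. The sample size and patient treatment do not change.
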